10.4. Descriptive Statistics

Subject specific PK parameter estimates will be listed ([Listing 28](#)). PK Estimates will be summarized ([Table 35](#), [Table 36](#)) by zoliflodacin dose. Summary statistics will include mean, SD, min, max, median, coefficient of variation as a percent (CV%), GM, and geometric SD (GSD). The individual ratio of exposure parameters (C_{max} , $AUC_{(0-last)}$ and $AUC_{(0-inf)}$) will be summarized by min, max, median, CV%, GM, and 95% CI (t-intervals using log-transformed parameters) ([Table 37](#)).

11. IMMUNOGENICITY

Not applicable.

12. OTHER ANALYSES

Not applicable.

13. REPORTING CONVENTIONS

The number of decimal places reported for listings and certain summary statistics (min and max) of height, weight, and safety parameters (clinical safety laboratory results, vital signs, etc.) will match the number of decimal places reported by the CTU, while other summary statistics (mean, median, GM, GSD) will be reported to an additional decimal place. Drug concentrations, AUCs, and C_{max} and their summary statistics will have the same number of significant digits as the drug concentrations reported by the bioanalytical laboratory. K_e will be reported to 3 decimal places. Other PK parameters will be reported to 1 decimal place. P-values ≥ 0.001 and ≤ 0.999 will be reported to 3 decimal places; p-values less than 0.001 will be reported as “ <0.001 .” Percentages (including CV) will be reported as whole numbers.

Listings of individual subject data include a Subject ID column. The subject identifiers assigned by site staff are replaced throughout this report with the Standard Data Tabulation Model (SDTM) variable USUBJID to protect the confidentiality of those who volunteered to participate in this protocol. USUBJID has been created as a composite of the 3-letter EDC platform code followed by a numeric identifier assigned chronologically to enrolled subjects as well as screening failures across all sites and protocols in the EDC platform. Any data sharing activities will include the USUBJID and not the subject identifiers assigned at the site.

14. TECHNICAL DETAILS

SAS version 9.4 or above or R versions 3.2 or above will be used to generate tables, figures, and listings. PK parameters will be estimated through a NCA using Phoenix[®] WinNonlin[®] version 8.0 or later (Pharsight Corporation, Cary, NC).

**15. SUMMARY OF CHANGES IN THE CONDUCT OF THE STUDY OR
PLANNED ANALYSES**

None to report.

17. LISTING OF TABLES, FIGURES, AND LISTINGS

Table, figure, and listing shells are presented in Appendices 1, 2, and 3.

APPENDICES

9.5.1 Efficacy/Immunogenicity and Safety Measurements Assessed and Flow Chart

Table 2: Schedule of Study Procedures

Study Visit	Screening ¹	Inpatient Periods 1-4			Outpatient Periods 1-4	Final Visit (after Dose 4)	Unscheduled	Early Termination
		Check-in	Dosing	Follow-up				
Study Day / Assessments	-21 to -2	-1	1	2	3 - 7	8 (± 2)		
Informed consent	X							
Inclusion/Exclusion criteria ²	X	X	X					
Demographics	X							
Medical history	X							
Medical history update		X						
Prior and Concomitant Medications ³	X	X	X	X	X	X	X	X
Complete PE ⁴	X					X		X
Abbreviated PE ⁵		X						
Symptom-directed PE ⁶			X	X			X	
Height, weight, BMI ⁷	X							
Weight		X				X		X
Vital signs ⁸	X	X	X	X		X	X	X
Clinical labs ⁹	X	X		X		X	X	X
Viral serology ¹⁰	X							
Serum pregnancy test ¹¹	X	X				X		X
Serum FSH level ¹¹	X							
Urine toxicology	X	X						
Alcohol urine test	X	X						
12-lead standard ECG ¹²	X	X	X	X		X	X	X
Continuous Holter ECG ¹³			X	X				
Randomization ¹⁴			X					
Study drug dosing			X					
PK samples ¹⁵			X	X				X
Counsel on use of appropriate contraception and avoidance of pregnancy ¹⁶	X			X		X	X	X
Counsel to avoid use of prohibited medications, alcohol, marijuana and illicit drugs	X			X				
Counsel to avoid rigorous physical activity	X	X		X				

Study Visit	Screening ¹	Inpatient Periods 1-4			Outpatient Periods 1-4	Final Visit (after Dose 4)	Unscheduled	Early Termination
		Check-in	Dosing	Follow-up				
Study Day / Assessments	-21 to -2	-1	1	2	3 - 7	8 (± 2)		
AE and SAE review ¹⁷			X	X	X	X	X	X
Admit to CTU		X						
Discharge from CTU				X				
Discharge from trial						X		

1. Screening is completed within 21 days before study drug dosing and may require more than one visit.
2. Inclusion/Exclusion criteria at Screening and on Day -1 and Day 1 before dosing in Dosing Period 1 to determine eligibility for enrollment and randomization. I/E criteria will be confirmed before each subsequent dosing period.
3. Prior Medications include prescription during the period 30 days before first dosing and non-prescription drugs, herbs, vitamins, and nutritional supplements taken during the period 15 days before first dosing. ConMeds include those taken after dosing. (See Section 6.6 of Protocol) for prohibited medications and exclusions).
4. Complete PE (except genital, breast, and rectal exams): at Screening, and Final Visit, or ET.
5. Abbreviated PE: on Day -1 (not performed if the complete PE was performed ≤7 days from this visit) in each inpatient period.
6. Symptom-directed PE: on Day 1 (pre-dose and post-dose) and Day 2 in each dosing period to evaluate new symptoms before dosing and AEs after dosing.
7. BMI is calculated as weight in kg divided by height (in meters) squared.
8. Vital signs at Screening; on Days -1, 1, and 2 in each dosing period; and at Final Visit after Dose 4, or ET. On Day 1 of each dosing period, VS at baseline (within 1 h before dosing) and at 1 h (±10 minutes), 2 h (±10 minutes), and 4 h (±10 minutes) after dosing.
9. Clinical laboratory testing with a minimum 4-h fast.
10. Viral serology (HIV1/2 test, HBsAg, HCV antibody): at Screening.
11. Serum pregnancy test in all women at Screening and within 24 h before each dosing period, and at the Final Visit, or ET. FSH only at Screening in postmenopausal women.
12. 12-lead standard ECG with 10-sec rhythm strip: at Screening, Day -1, Day 1 [within 1 h before dosing, and at 1 h (±10 minutes), 2 h (±10 minutes), and 4 h (±10 minutes) after dosing], Day 2 (24 h ±2 h) or ET. At an Unscheduled Visit, a 12-lead standard ECG will be done only if needed for the evaluation of an AE.
13. Continuous Holter ECG recorded from 1 h before dosing to 24 h after dosing in each dosing period. ECGs are extracted (three replicates per timepoint) before dosing (at 45, 30, and 15 minutes before dosing) and at 0.5 h, 1 h, 2 h, 3 h, 4 h, 6 h, 8 h, 12 h, and 24 h after dosing in each dosing period.
14. Eligible subjects are randomized to a treatment sequence on Day 1 before receiving Dose 1. Randomization confirmed at each dosing period.
15. Blood (plasma) PK samples: within 30 minutes before dosing, and at 0.5 h (±5 minutes), 1 h (±5 minutes), 2 h (±5 minutes), 3 h (±10 minutes), 4 h (±10 minutes), 6 h (±10 minutes), 8 h (±15 minutes), 12 h (±15 minutes), and 24 h (±2 h) after dosing in each dosing period, or ET if it occurs within 24 h of dosing.
16. Female subjects to use appropriate contraception and avoid pregnancy for 30 days after Final Visit or ET. Male subjects to use appropriate contraception and avoid donating sperm for 90 days after Final Visit or ET.
17. Collect all AEs from the time of dosing in Dosing Period 1 through Final Visit after Dose 4. Follow up AEs and SAEs to resolution or stabilization in the clinical judgment of the study investigator.

12.2.2 Displays of Adverse Events**Table 3: Toxicity Grading Tables – Clinical Adverse Events**

Clinical AEs	Mild (Grade 1)	Moderate (Grade 2)	Severe (Grade 3)
Vital Signs			
Fever - °C	38.0-38.4	38.5-38.9	>38.9
Fever - °F	100.4-101.1	101.2-102.0	>102.0
Tachycardia - bpm	101-115	116-130	>130 or ventricular dysrhythmias
Bradycardia - bpm	50-54 OR 45-50 if baseline <60	45-49 OR 40-44 if baseline <60	<45 OR <40 if baseline <60
Hypertension (systolic) - mmHg	141-150	151-160	>160
Hypertension (diastolic) - mmHg	91-95	96-100	>100
Hypotension (systolic) - mmHg	85-89	80-84	<80
Tachypnea – breaths per minutes	23-25	26-30	>30
12-Lead Standard ECG			
QTcF interval prolonged (msec)	Asymptomatic, QTcF 450-479 msec	Asymptomatic, QTcF 480-500 msec OR increase in interval 30-59 msec above baseline	Asymptomatic, QTcF >500 msec OR increase in interval ≥60 msec above baseline
PR interval prolonged (msec)	210-250 msec	>250 msec	Type II 2 nd degree AV block OR ventricular pause >3.0 sec
Cardiovascular			
Arrhythmia		Asymptomatic or transient signs; no medical intervention required	Recurrent and/or persistent signs; symptomatic medical intervention required
Hemorrhage	Estimated blood loss ≤100 mL	Estimated blood loss >100 mL; no transfusion required	Blood transfusion required
Respiratory			
Cough	Transient cough; no treatment required	Persistent cough; treatment required	Interferes with daily activities
Bronchospasm, Acute	Transient bronchospasm; no treatment required; forced expiratory volume in one second (FEV1) 71-80% of predicted peak flow	Requires treatment; normalizes with bronchodilator; FEV1 60-70% of predicted peak flow	No normalization with bronchodilator; FEV1 <60% of predicted peak flow
Dyspnea	Does not interfere with usual and social activities	Interferes with usual and social activities; no treatment	Prevents usual and social activities OR requires treatment
Gastrointestinal			
Nausea	No interference with normal activity	Some interference with normal activity	Prevents daily activities
Vomiting	No interference with activity OR 1-2 episodes in a 24 h period	Some interference with activity OR >2 episodes in a 24 h period	Prevents daily activity OR requires medical intervention

Clinical AEs	Mild (Grade 1)	Moderate (Grade 2)	Severe (Grade 3)
Diarrhea	2-3 loose or watery stools in a 24 h period	4-5 loose OR watery stools in a 24 h period	6 or more loose or watery stools in a 24 h period OR requires IV hydration OR requires medical intervention
Oral Discomfort / Dysphagia	Mild discomfort; no difficulty swallowing	Some limits on eating /drinking	Eating/talking very limited; unable to swallow solid foods
Local IV Catheter Reaction			
IV site reaction	Not applicable	Erythema with associated symptoms (e.g., edema, pain, induration, phlebitis)	Ulceration or necrosis; severe tissue damage; operative intervention indicated
Systemic Reactions			
Anaphylaxis	--	--	Symptomatic bronchospasm, with or without urticaria; parenteral intervention indicated; allergy-related edema or angioedema; hypotension
Allergic Reaction	Pruritus without rash	Localized urticaria OR requires oral therapy	Generalized urticaria OR angioedema OR anaphylaxis OR requires epinephrine
Hypersensitivity (including drug fever)	Transient flushing or rash; temperature 38.0-38.4 °C (100.4-101.1 °F)	Rash; flushing; urticaria; dyspnea; temperature 38.5 - 38.9 °C (101.2 – 102.0 °F)	Symptomatic bronchospasm with or without urticaria; parenteral medication indicated; allergy-related edema or angioedema; hypotension; temperature >38.9 °C (>102.0 °F)
Headache	No interference with activity	Repeated use of non-narcotic pain reliever for more than 24 h OR some interference with activity	Significant; any use of narcotic pain reliever OR prevents daily activity OR requires triptans
Fatigue	No interference with activity	Some interference with activity	Significant; prevents daily activity
Myalgia	No interference with activity	Some interference with activity	Significant; prevents daily activity
Skin			
Mucocutaneous	Erythema, pruritus	Diffuse, maculo-papular rash, dry desquamation	Vesiculation OR moist desquamation OR ulceration
Pruritus	No or minimal interference with usual social and functional activities	Greater than minimal interference with usual social and functional activities	Inability to perform usual social and functional daily activities

Clinical AEs	Mild (Grade 1)	Moderate (Grade 2)	Severe (Grade 3)
All Other Conditions			
Illness or clinical AE (as defined according to applicable regulations)	Require minimal or no treatment; does not interfere with the subject's daily activities.	Result in a low level of inconvenience or concern with therapeutic measures; may cause some interference with functioning.	Interrupt a subject's usual daily activity and may require systemic drug therapy or other treatment; are usually incapacitating

12.4.1 Individual Laboratory Measurements and Abnormal Laboratory Values**Table 4: Laboratory Adverse Event Grading Scale**

Laboratory AEs	Mild (Grade 1)	Moderate (Grade 2)	Severe (Grade 3)
Chemistry			
Sodium decrease – mmol/L	130 - 131	125 –129	<125
Sodium increase – mmol/L	149 - 150	151 – 153	>153
Potassium increase – mmol/L	5.6 – 6.0	6.1 – 6.4	≥6.5
Potassium decrease – mmol/L	3.0 – 3.2	2.5 – 2.9	<2.5
Bicarbonate (CO ₂) increase – mmol/L	34 – 35	36 – 37	>37
Bicarbonate (CO ₂) decrease – mmol/L	17 - 18	14 - 16	<14
Glucose decrease, fasting – mg/dL	47 - 49	45 –46	<45
Glucose increase, fasting – mg/dL	116 – 125	126 – 249	≥250
Glucose increase, non-fasting – mg/dL	116 – 160	161 – 249	≥250
Blood urea nitrogen – mg/dL	25 - 27	28 – 32	>32
Creatinine increase, male – mg/dL	1.46 – 1.70	1.71 – 2.30	>2.30
Creatinine increase, female – mg/dL	1.21 – 1.50	1.51 – 2.00	>2.00
Calcium decrease – mg/dL	7.8 – 8.0	7.0 – 7.7	<7.0
Calcium increase – mg/dL	11.0 – 11.4	11.5 – 12.4	≥12.5
Total protein decrease – g/dL	5.1 – 5.7	4.6 – 5.0	<4.6
Albumin decrease – g/dL	2.8 – 3.4	2.5 – 2.7	<2.5
AST increase, male – U/L	46 – 115	116 – 220	>220
AST increase, female – U/L	36 - 90	91 - 175	>175
ALT increase, male – U/L	53 – 115	116 - 230	>230
ALT increase, female – U/L	39 – 95	96 – 190	>190
Alkaline phosphatase increase – U/L	151 – 240	241 – 360	>360
Total bilirubin (serum) increase – mg/dL (with other LFTs in the normal range)	1.5 – 2.0	2.1 – 2.5	>2.5
Total bilirubin (serum) increase – mg/dL (accompanied by a >3 x ULN increase in ALT or AST)**	1.5 – 1.7	1.8 – 2.1	>2.1
Hematology			
Hemoglobin decrease, female – g/dL	10.8 – 11.2	9.4 – 10.7	<9.4
Hemoglobin decrease, male – g/dL	11.8 – 12.9	10.0 – 11.7	<10.0
WBC increase – cells/μL	11,000 – 15,000	15,001 – 20,000	>20,000
WBC decrease – cells/μL	2,500 – 3,500	1,500 – 2,499	<1,500
Neutrophils decrease – cells/μL	1,200 – 1,499	1,000 – 1,199	<1,000
Lymphocytes decrease – cells/μL	750 – 849	500 – 749	<500
Monocytes increase – cells/μL	1,101 – 2,000	2,001 – 3000	>3,000
Eosinophils increase – cells/μL	500 – 750	751 – 1,500	>1,500
Basophils increase – cells/μL	201 – 500	501 – 800	>800
Platelets decrease – cells/μL	120,000 – 124,000	100,000 – 119,000	<100,000

Laboratory AEs	Mild (Grade 1)	Moderate (Grade 2)	Severe (Grade 3)
Urinalysis			
Protein	1+	2+	>2+
Glucose	1+	2+	>2+
Blood (dipstick)	1+	2+	>2+
Blood (microscopic) – RBCs per HPF	6-10	11-50	>50 and/or gross blood
WBC (microscopic) – WBC per HPF	5-10	11-50	>50
Bacteria (microscopic)	few	moderate	many

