Note: Clinically significant abnormal ECG results include: complete left or right bundle branch block; other ventricular conduction block; 2nd degree or 3rd degree atrioventricular (AV) block; sustained atrial or ventricular arrhythmia; two premature ventricular contractions in a row; pattern of ST elevation felt consistent with cardiac ischemia; evidence of a previous myocardial infarction (MI), left ventricular hypertrophy (LVH), or more than minor non-specific ST-T wave changes; any characteristics that would make QT assessment unreliable, including flat T waves; or any condition deemed clinically significant by a study investigator
- 9) Abnormal renal function

Note: Normal renal function is defined as normal creatinine [per criteria in [Appendix B](#)] and normal estimated glomerular filtration rate (eGFR) [i.e., >80.0 mL/min] values according to Cockcroft-Gault
- 10) Positive serology results for HIV, HBsAg, or HCV
- 11) Febrile illness with temperature $\geq 38.0^{\circ}\text{C}$ for <7 days before dosing in each treatment period
- 12) Donated whole blood or blood products within 60 days before first dosing, or plans to donate or receive before Final Visit (Day 8 \pm 2 after last dose in dosing period 4)

-
- *Note: Blood products include RBCs, white blood cells (WBCs), platelets, and plasma*
- 13) Known allergic reactions to fluoroquinolones or to components present in the formulation or processing of zoliflodacin and moxifloxacin
- 14) Treatment with another investigational product within 30 days of first dosing or 5 half-lives or twice the duration of the biological effect of the study drug (whichever is longer)
- *Note: Investigational products include a drug, vaccine, biologic, device, or blood product*
- 15) Active drug or alcohol binge consumption, abuse, or dependence within 12 months before Screening Visit that, in the opinion of the investigator, would interfere with adherence to study requirements
- 16) Use of any prescription medication within 30 days before first dosing or planned use during the trial except as noted below and approved by the designated study clinician

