 - Any new or prior grade 3 AEs that were judged unrelated to study drug should be either resolved or downgraded to Grade 1 and in the opinion of the site principal investigator or appropriate sub-investigator, the AEs, individually or in cluster do not pose a risk to the subject or would be likely to confound interpretation of the results.

If a subject has a Grade 3 AE judged related to study drug administration, this subject will be withdrawn from the study and will not receive subsequent dosing. For all other AEs, dosing may be delayed up to 14 days in order to follow the AE for downgrading or resolution according to the above. If the subject does not meet the criteria for dosing specified above in 14 days, this subject will be withdrawn from the study and will not receive subsequent dosing.

After admission to the CTU, the subject will fast at least 8 h before dosing but will have access to water during that period.

7.4 Inpatient period (Days 1-2 in each dosing period) (Overall, Days 1-2, 9-10, 17-18, and 25-26 for dosing periods 1, 2, 3 and 4, respectively)

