9.5 Halting Rules

9.5.1 Study Halting Criteria

9.5.1.1 Halting Criteria for Zoliflodacin and Placebo Periods

Study dosing of zoliflodacin or placebo will be temporary halted, and a review of available safety data will be conducted by the SMC if any of the following occur after dosing:

1. Death of a subject following dosing regardless of relatedness to the study drug;
2. One subject with a non-fatal SAE that is considered related to the study drug by the study PI or authorized physician (listed in FDA Form 1572);
3. Two or more subjects experience a QTcF >500 msec or ≥ 60 msec above baseline, based on readings from at least two standard 12-lead ECGs after study drug administration;
4. Two or more subjects with a Grade 3 systemic AE coded in the same organ system that is considered related to the study drug by the study PI or authorized clinician;

Note: VS abnormalities will be considered part of a systemic disorder or an organ-specific condition, as described in Appendix C: Adverse Events Toxicity Grading Criteria

, in order to be included among the Study Halting Criteria.

5. One subject experiences a symptomatic ventricular tachyarrhythmia with or without QTcF prolongation after study drug administration;
6. An overall pattern of symptomatic, clinical non-serious events that may appear minor in terms of individual events, but that may collectively represent a serious potential safety concern and pose a risk to continuing a subject in the trial.

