9.5.1.2 Halting Criteria for Moxifloxacin Periods

Study dosing of moxifloxacin will be temporary halted, and a review of available safety data will be conducted by the SMC if any of the following occur after dosing:

1. Death of a subject following dosing regardless of relatedness to moxifloxacin;
2. One subject with a non-fatal SAE that is considered related to moxifloxacin by the study PI or authorized physician (listed in FDA Form 1572);
3. Three or more subjects with a Grade 3 systemic AE coded in the same organ system that is considered related to moxifloxacin by the study PI or authorized clinician.

Note: VS abnormalities will be considered part of a systemic disorder or an organ specific condition, as described in Appendix C: Adverse Events Toxicity Grading Criteria
, in order to be included among the Study Halting Criteria.

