Appendix C: Adverse Events Toxicity Grading Criteria

ABBREVIATIONS: Abbreviations utilized in the Table:

LLN = Lower Limit of Normal

Req = Required

IV = Intravenous

Dec = Decreased

ESTIMATING SEVERITY GRADE

For abnormalities NOT found elsewhere in the Toxicity Tables, use the scale below to estimate grade of severity:

GRADE 1	Mild	Events require minimal or no treatment; do not interfere with the subject's daily activities.
GRADE 2	Moderate	Events result in a low level of inconvenience or concern with therapeutic measures; may cause some interference with functioning.
GRADE 3	Severe	Events interrupt a subject's usual daily activity and may require systemic drug therapy or other treatment; are usually incapacitating.

SERIOUS OR LIFE-THREATENING AEs

Clinical events considered to be serious or life-threatening include, but are not limited to: seizures, coma, tetany, diabetic ketoacidosis, disseminated intravascular coagulation, diffuse petechiae, paralysis, acute psychosis, and severe depression.

COMMENTS REGARDING THE USE OF THESE TABLES

- Standardized and commonly used toxicity tables (Division of AIDS, National Cancer Institute [NCI] Common Toxicity Criteria [CTC], and World Health Organization [WHO]) have been adapted for use by the Division of Microbiology and Infectious Diseases (DMID) and modified to better meet the needs of subjects in DMID trials.
- For parameters not included in the following Toxicity Tables, the CTU will refer to the "Guide for Estimating Severity Grade" located above.
- Criteria are generally grouped by body system.

Some protocols may have additional protocol specific grading criteria, which will supersede the use of these tables for specified criteria.

Table 7: Toxicity Grading Tables – Clinical AEs

Toxicity Grading Tables				
Clinical AEs	Mild (Grade 1)	Moderate (Grade 2)	Severe (Grade 3)	Comments
VITAL SIGNS				
Fever - °C	38.0-38.4	38.5-38.9	>38.9	No recent hot or cold beverages or smoking. A protocol should select either °C or °F for inclusion
Fever - °F	100.4-101.1	101.2-102.0	>102.0	
Tachycardia - bpm	101-115	116-130	>130 or ventricular dysrhythmias	Assume awake and in supine position for 5 min at rest; for AE, measurements at least 3 times with 2 concordant results (Section 8.1.6)
Bradycardia – bpm • Baseline >60 OR, if • Baseline <60	• 50-54 OR, if Baseline <60, • 45-50	• 45-49 OR, if baseline <60, • 40-44	• <45 OR, if baseline <60 • <40	As above

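### The toxicity tables do not name third-degree AV block, so a transient, untreated case can be graded one step below type II second-degree block and miss the Grade 3 safety triggers

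*SAP*

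**What the plan says.** Protocol Appendix C Table 9 and SAP Table 3 grade PR prolongation in the same way. A PR of 210-250 msec is Grade 1 and anything above 250 msec is Grade 2. Grade 3 is a type II 2nd "degree AV block OR ventricular pause >3.0 sec". That entry has no symptom qualifier, whereas each grade of the QTcF row opens with one.

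The Cardiovascular part of the clinical AE table (Protocol Table 7, repeated in SAP Table 3) has an Arrhythmia row with no Grade 1 entry. Its Grade 2 entry is "Asymptomatic or transient signs; no medical intervention required". Its Grade 3 entry covers recurrent or persistent signs, or symptoms needing medical intervention.

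Third-degree block appears in neither grading table. It is named in Protocol 5.2, exclusion criterion 8, where "2nd degree or 3rd degree atrioventricular (AV) block" is listed among clinically significant abnormal ECG results.

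Two rules act on Grade 3:
- Protocol 7.3: "If a subject has a Grade 3 AE judged related to study drug administration, this subject will be withdrawn from the study".
- Protocol 9.5.1.1, criterion 4, halts zoliflodacin and placebo dosing for "Two or more subjects with a Grade 3 systemic AE coded in the same organ system", if considered related. Protocol 9.5.1.2, criterion 3, halts moxifloxacin dosing for "Three or more subjects with a Grade 3 systemic AE coded in the same organ system", also if related.

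**The concern.** Third-degree block is the more advanced conduction failure, and exclusion criterion 8 treats it as at least as disqualifying as second-degree block. A severity scale should not rank it lower. Because the PR row names only the lesser block, the grade of the more advanced one depends on how the episode presents: whether it recurs, persists, causes symptoms or needs treatment.

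The grade matters because the other automatic rules do not reach a non-serious AV block. The remaining halting criteria for zoliflodacin and placebo are death, a related SAE, QTcF prolongation, symptomatic ventricular tachyarrhythmia and a pattern of symptomatic events. Moxifloxacin periods have only death, a related SAE and the Grade 3 count. For a non-serious, asymptomatic AV block, the Grade 3 count is therefore the only automatic route to a halt, and a related Grade 3 is the only automatic route to withdrawal.

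**Working it through.** The plan gives no figure to reproduce. The check applies the written rules to two blocks with the same presentation: one transient episode, no recurrence, no symptoms, no intervention, no ventricular pause over 3.0 sec, heart rate outside Grade 3 bradycardia (below 45 bpm, or below 40 bpm if baseline is under 60), not an SAE, and judged related to study drug.

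| Step | Type II second-degree block | Third-degree block |
|---|---|---|
| PR row (Protocol Table 9, SAP Table 3) | Named: Grade 3 | Not named, no pause over 3.0 sec: not Grade 3 |
| Arrhythmia row (Protocol Table 7, SAP Table 3) | Not needed | Transient, no intervention: Grade 2 |
| Resulting grade | 3 | 2 |
| Automatic withdrawal (Protocol 7.3) | Yes | No |
| Contribution to halting count (Protocol 9.5.1) | 1 | 0 |

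Grade gap: 3 - 2 = 1, in the wrong direction.

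Effect on the halting rule, assuming all events are related and coded in the same organ system:
- Zoliflodacin or placebo periods, threshold 2. One subject with type II second-degree block and one with third-degree block count 1 + 0 = 1, so there is no halt. With third-degree block at Grade 3 the count is 1 + 1 = 2, and dosing halts.
- Two subjects with third-degree block count 0 + 0 = 0 now, and 1 + 1 = 2 if the table names it.
- Moxifloxacin periods, threshold 3. Three subjects with third-degree block count 0 now, and 3 if the table names it.

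A third-degree block already reaches a stronger rule if there is a pause over 3.0 sec, if it recurs or persists, if symptoms need intervention, if heart rate falls into Grade 3 bradycardia, or if it is an SAE. One related SAE halts dosing. The gap is confined to the presentation set out above.

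**The case against.** The strongest reply is that several provisions already catch the event.
- Eligibility is re-confirmed before every dose (Protocol 7.3 and 7.4.2). Exclusion 8 names third-degree block, and exclusion 2 bars a history of cardiac arrhythmia, which arguably covers a block that has resolved.
- A Grade 2 AE must resolve or fall to Grade 1, and the investigator must judge that it poses no risk, before the next dose.
- Protocol 5.3.3 lets the investigator remove a subject for any AE warranting it. Protocol 9.2.2 allows the event to be made an SAE as an important medical event. The SMC can meet ad hoc.
- Severity is a clinician's judgment (Protocol 9.2.3), and few clinicians would rate complete block below type II second-degree block.

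All of this stands, and a recognised block would get medical review. These provisions largely protect the individual subject. They do not add that subject to the Grade 3 count, and most depend on discretion where the Grade 3 rules do not.

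Two stronger readings are tempting and are not supported.

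A reader might infer that the block could fall to Grade 1, a two-grade gap, through the general scale in Appendix C, where Grade 1 begins "Events require minimal or no treatment; do not interfere with the". That scale is limited by its own opening: "For abnormalities NOT found elsewhere in the Toxicity Tables, use the scale below to estimate grade of severity". Once third-degree block is read as an arrhythmia it is found elsewhere, in a row with no Grade 1, so the two routes are not open together.

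A reader might also infer that the Severe cells for PR in SAP Table 28 must always print zero, because no PR value in msec maps to Severe. The documents do not establish this. The CRF is not among them, so a coded block or pause field cannot be ruled out. RR interval is a collected standard-ECG parameter (SAP 4.5), and whether it could flag a pause is untested. The Table 28 implementation note also reduces the PR block to one row when no PR event is graded. No event would be lost in any case: block and pause can appear in the AE tables, Listing 18 and the Holter morphology summaries.

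**Conclusion.** The point holds in a narrow form. Read through the Arrhythmia row, a related, transient, non-recurrent, untreated third-degree AV block is Grade 2, while type II second-degree block with the same presentation is Grade 3. The cost is one grade, the automatic withdrawal of that subject, and one unit in a halting count with a threshold of 2 or 3.

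This rests on three assumptions: that third-degree block is classed as an arrhythmia, that the grader follows the row as written, and that an AV block counts as a systemic AE under the halting criteria. The documents give no expected rate of AV block, and entry criteria exclude known second- or third-degree block and PR above 209 msec, so no probability can be attached. It is a minor correction, worth making because it removes an inverted ordering from a safety rule at almost no cost. The primary QTcF analysis and the sample size are not affected.

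**What to change.** In Protocol Table 9 and SAP Table 3, insert *or 3rd degree* after the second-degree term in the PR Grade 3 entry, leaving the pause alternative as it is. Add one sentence stating that this row governs AV block over the Arrhythmia row.

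The cost is a few words in one cell of two tables, plus that sentence. Table 9 is part of the Protocol, so the change goes through an amendment (Protocol 14.2). No new data, programming or change to the primary analysis is needed, and Table 28 can stay as it is.
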